**Investigation Code** **Granulox01** **Final Version** **Approval date** **2019-10-24**

Site visits	Run-in Visit	Home care	Visit 1	Home care	Visit 2	Home care	Visit 3	Home care	Visit 4	Home care	Visit 5	Home care	Visit 6	Home care	Visit 7	Final Visit a)	Extra visit
Time frames	D-14	D-14-D0	D0	(At least every 3 rd day)	W1 (Day 7 ±1 day)	At least every 3 rd day	W4 (Day 28 ±3 days)	At least every 3 rd day	W8 (Day 56 ±3 days)	At least every 3 rd day	W12 (Day 84 ±3 days)	At least every 3 rd day	W16 (Day 112 ±3 days)	At least every 3 rd day	W20 (Day 140 ±3 days)		
Reason(s) study arrest																X	

a) To be completed in any case (premature arrest, CCC).  
b) Assessment of wound healing and wound progress/evolution completed after patient's study termination and based on patient-series of wound pictures.  
[REDACTED]  
[REDACTED]  
e) Safety monitoring including reporting of adverse events, serious adverse events, adverse device effects, serious adverse device effects, and device deficiencies.

### **3.4 Subject Population**

The study population is comprised of N = 254 adult patients presenting with VLUs who meet the study's inclusion and exclusion criteria. Approximately equal proportions of male and female patients will be enrolled in the study.

#### **3.4.1 Inclusion Criteria**

All of the following criteria need to be fulfilled for inclusion in the study:

1. Signed consent to participate.
2. No planned hospitalization in the forthcoming 20 weeks.
3. Male or female (women of childbearing age must have an acceptable method of birth control).
4. Age >18 years.
5. Recent (less than 12 months) doppler or duplex colour ultrasonography compatible with chronic venous insufficiency.
6. ABPI (less than 3 months)  $\geq 0.7$  for both legs. If ABPI  $>1.4$ , then big toe pressure  $>60$  mmHg is required or an alternative measurement verifying normal distal arterial flow.
7. At least one or more supra- or peri-malleolar leg ulcers and no foot ulcer or another chronic wound.
8. In case of two ulcers, select ulcer with the highest PUSH score at randomization and treat the non-selected ulcer in the same way as ulcers in the control group.
9. In case of two ulcers on the same limb, ensure that the distance between each ulcer is 3 cm as measured from the margins of each ulcer that are closest to one another.
10. Wound duration  $>8$  weeks and  $<60$  months.
11. At randomization, the ulcer area should be  $3 \text{ cm}^2 - 70 \text{ cm}^2$  and should not have decreased by more than 30% during the 2-week run-in period.
12. Less than 50% of the wound area should be covered with fibrinous tissue at randomization and after debridement.
13. Patients considered as compliant/adherent to the compression device during the run-in period (i.e. no more than 2 days without compression over the 2-week run-in period).
14. No clinically significant comorbidities requiring the use of systemic steroids or any cytotoxic or immunosuppressive agents.

#### **3.4.2 Exclusion Criteria**

If any of the following criteria applies, the patient will be excluded from participation:

1. Infected ulcer according to the judgment of the investigator defined as any wound condition requiring the prescription or continuation of systemic antibiotic therapy at randomization.
2. Circumferential wounds.

3. Wound covered fully or partially by necrotic tissue (black tissue).
4. Patients who will have problems following the protocol, especially compression therapy.
5. Patients included in another on-going clinical investigation, or patients who have participated in a clinical investigation during the past 30 days.
6. Wounds treated with dressings containing an active component (e.g. silver, nano-oligosaccharide factor (NOSF), charcoal, chlorhexidine, iodine or ibuprofen) 14 days prior to study enrollment.
7. Patient with a systemic infection not controlled by suitable antibiotic treatment.
8. Current treatment with radiotherapy, chemotherapy, immunosuppressant drugs or high doses of oral corticosteroids (>10 mg Prednisolone or equivalent) if any.
9. Patient with deep vein thrombosis within 3 months prior to inclusion.
10. Known allergy/hypersensitivity to the ingredients of the dressings and/or Granulox®.
11. Malignant wounds.
12. Endovenous surgery planned or performed within the past 30 days.
13. Primary lymphoedema caused by congenital/developmental defect, i.e. Milroy's disease (congenital lymphedema), Meige's disease (lymphedema praecox), or Late-onset lymphedema (lymphedema tarda).

### **3.4.3 Method of Assigning Subjects to Treatment Groups**

At initial screening and after an informed consent signature is obtained (day-14), an enrolment number is assigned to each patient who agrees to take part in the study. Following the run-in period, and after all eligibility criteria have been confirmed (day 0), randomisation is initiated and treatment allocated to either standard of care only (control group) or standard of care and Granulox® (test group).

Randomisation is centralized and stratified according to:

- Wound duration (<5 months;  $\geq$ 5 months)
- Wound area after run-in period ( $<10 \text{ cm}^2$ ;  $\geq 10 \text{ cm}^2$ )
- Country

### **3.4.4 Withdrawal of Subjects from Treatment or Assessment**

Subjects are free to discontinue participation in the study at any time, and without prejudice to further treatment. Subjects who withdraw from the study should always be asked about the reason(s) for their discontinuation and about the presence of any Adverse Event/Adverse Device Effect or Device Deficiency and, if possible, be assessed by the Principal Investigator. Each reported Adverse Event/Adverse Device Effect will be followed up.

Subjects may be withdrawn from the study at any time, at the discretion of the Principal Investigator.

Incorrectly enrolled or randomised subjects will be withdrawn from the study. A subject may, however, continue study involvement under special circumstances (i.e. if continuation of study-related treatment or follow-up actions are necessary for the subject's safety and well-being, or if only a follow-up period remains, and the continuation of the subject's study involvement is not expected to be associated with any risk or discomfort for the subject).

### **3.5 Investigational Device**

#### **3.5.1 Summary description of the Investigational Device(s) and Comparator(s)**

##### **3.5.1.1 Investigational Device**

The investigational device is Granulox®, a topical haemoglobin spray, which is designed to transport oxygen to the wound site. Granulox® is intended to increase oxygen supply to the wound. Granulox is a CE marked medical device manufactured by HÄLSA Pharma GmbH (report number: 12911FS06F). It is an innovative product for the treatment of chronic wounds, such as venous leg ulcer, arterial leg ulcer, mixed leg ulcer, diabetic foot ulcers, secondary healing of surgical wounds and pressure sores. Granulox can also be used on sloughy and infected wounds.

The mode of action is that once Granulox® is sprayed, the haemoglobin starts to bind oxygen from the atmosphere and the process of oxygen transportation begins. Oxygen promotes the formation of new blood vessels and subsequently the growth of new skin. Granulox provides the wound with the required oxygen by means of diffusion. The active substance haemoglobin supplies the base of the wound with external oxygen. The improved oxygen supply to the base of the wound supports wound healing.

Granulox® should not be used simultaneously with topical medicines for your wound, such as application of local antibiotics, as interactions have not yet been studied sufficiently. Disinfectants are known to impair the efficacy of Granulox®. Therefore, after application of a disinfectant, the area must be subsequently flushed thoroughly with a physiological solution. Thorough flushing with a physiological solution is necessary after use of proteolytic (enzymatic) debridement.

In this study, Granulox® will be used as intended, in combination with an appropriate foam or wound contact layer wound dressing and in addition to defined standard care.

#### **Granulox®:**

The instructions for use for Granulox® should be consulted before initiating treatment. The following procedural steps should be followed:

1. After wound bed preparation (e.g. debridement and cleaning) Granulox® should be sprayed onto the cleaned wound until the wound is completely coated with a thin film. That is, hold the nozzle about 5 to 10 cm from the wound and spray until the wound is completely coated with a thin film. 1 to 2 seconds are normally sufficient to cover a wound area of 2 x 3 cm.
2. After Granulox® has been applied, the wound should be covered with a breathable wound dressing containing no active ingredients.
3. Granulox® should be applied again every time the dressing is changed, but at least every three days.

#### **Defined standard of care:**

VLU standard of care treatment will be performed according to local practice requirements but reapplied at least every third day until complete epithelization. Standard of care will include the following:

1. Wound bed preparation, i.e.:

- Careful wound cleansing with saline/water or Ringer's solution or preserved mechanical wound cleansers (i.e. polyhexanide (Prontosan, Lavanid), or hypochlorous (Granudacyn, Microdacyn) irrigation)
- Wound debridement if necessary and as per standard of care (e.g. mechanical or surgical debridement)

2. Application of appropriate breathable wound dressing which must be selected among the following categories and with regard to routine local care, level of exudate, and healing stage:

- Hydrofiber: [REDACTED]
- Foam dressings: [REDACTED]  
[REDACTED]
- Wound Contact layer: [REDACTED]
- Superabsorbant: [REDACTED]

NB: Dressings including active components are not allowed. Within a clinic, there must be consistency in the choice in dressings, i.e. the same sequence of dressings should be kept for all the patients.

3. Application of appropriate compression therapy which must be selected among the following categories and with regard to routine local care, level of exudate, and healing stage:

- Multilayer compression: [REDACTED]
- Hosiery and stockings compression: [REDACTED]  
[REDACTED]
- Short stretch bandages

NB: A multilayer compression system is preferred and consistency in compression therapy throughout the study is mandatory, unless patient compliance issues necessitate change. Patients must be withdrawn from study in case of severe non-compliance to compression therapy.

All performed local care has to be documented in patients' medical records.

### **3.5.1.2 Comparator**

The control group will use the same defined standard of care as the treatment group (see section 3.5.1.1) but without Granulox®.

### **3.5.2 Labelling**

### **3.5.3 Device Accountability**

Mölnlycke and the Principal Investigator will keep records documenting the location of all investigational devices from shipment of investigational devices to the investigation site until return. This will be documented by a shipment log stored by Mölnlycke and in a device accountability log at the investigation site. The device accountability log at each investigational site will include information on; date, serial and batch number of delivered devices, date and subject identification for used devices, date, serial and batch numbers of devices returned.

The Site Monitor will verify the accountability process at each site during the site monitoring visits.

### 3.5.4 Storage conditions

During use, Granulox® can be stored at room temperature (max. 25 °C) until it is empty or up to 6 weeks. For long-term storage, place Granulox® in a refrigerator at temperatures from 2 °C to 8 °C.

Storage conditions for other components used in the study should follow instructions for use specific to each component.

### 3.6 Concomitant Treatments

Medication and treatment, which is considered necessary for the subject's safety and well-being, may be given at the discretion of the Principal Investigator. All concomitant medication and relevant treatment must be recorded in the appropriate section of the Case Report Form (CRF).

The following restrictions and specific considerations apply for the study:

- No use of local antiseptics will be authorized.
- Peri-wound skin cares may use emollients if necessary.
- Use of antibiotics and analgesics must be recorded on the appropriate CRF during the study.

### 3.7 Risks and benefits of the Investigational Device and clinical investigation

The following events have been identified as anticipated effects of Granulox®:

- In the overall evaluation of safety, the use of Granulox® for the treatment of chronic hypoxic wounds with poor blood supply as well of burn wounds and infected or critically colonized wounds is found to be safe and well-tolerated.
- Tests for cytotoxicity, sensitization, irritation and subcutaneous reactivity did not identify any hazardous properties and thus confirmed the safety of the topical haemoglobin spray. Tissue tolerability has also been tested using the semi-in-vivo method HET-CAM (hen's egg test on the chorioallantoic membrane) without any signs of irritation. The risk of inhaling aerosols when using Granulox® spray has been evaluated by Holzer et al. who concluded that there is no risk of inhaling nanoparticles or being exposed to harmful concentrations and that all ingredients can be degraded and excreted by the human body through natural pathways.
- Only one of the reviewed publications from previous clinical trials reported of adverse events (one event of infection) associated with topical administration of Granulox®. The majority of the evaluated publications explicitly stated no occurrence of adverse events.e.g.15,22,23
- Within the framework of the clinical investigation carried out at the Hospital Civil de Ciudad Victoria by the Mexican health government, the haemoglobin spray was applied almost 1,500 times on chronic wounds. In all cases, the spray was well tolerated and there were no undesirable events that might have resulted due to the application of the haemoglobin spray. In addition, Granulox® was rated as very easy to handle from the participants of the clinical trials under review.

The possible benefits associated with Granulox® are as follows:

- Higher healing rate / wound closure.
- Pain reduction.

- Reduced recurrence of slough.
- Improved health-related quality of life.

In summary, the single ingredients of Granulox® are established as safe for use in topical applications and the general safety and tolerability of Granulox® is assessed as very good.

## 4. DATA QUALITY ASSURANCE

### 4.1 *Monitoring, Audits and Inspections*

During the investigation, the Site Monitor will have regular contacts with the investigation site. These contacts will include monitoring visits, conducted in accordance with a clinical investigation specific monitoring plan, to confirm that the facilities remain adequate to specified standards and that the investigation site team is carrying out the procedure as stated in the Clinical Investigation Plan and supporting the Principal Investigator appropriately. All data must be accurately recorded in the CRF. Source data verification (a comparison of data in the CRF with the subject's hospital/practice and other records at the investigation site) with direct access to records will also be performed.

The Site Monitor or other Mölnlycke personnel will be available between visits if the Principal Investigator or other staff at the site needs information and/or advice.

Authorised representatives of Mölnlycke and/or a Regulatory Authority (RA) and/or the Ethics Committee (EC)/Institutional Review Board (IRB) may visit the investigation site to perform audits/inspections, including source data and informed consent verification.

### 4.2 *Training of Staff*

The Principal Investigator will ensure that appropriate training relevant to the investigation is given to the medical, nursing and other staff at the sites involved and that new information of relevance to the performance of this investigation is forwarded to the staff involved in a timely manner.

### 4.3 *Data Management*

The Data Management process includes all activities related to data handling regarding:

- Compilation of a CRF
- Randomisation
- Set-up of eCRF/database
- Specification of on-line checks
- Data entry/data editing
- Export of data from eCRF/database to analysis software
- Creation of post-entry checks and listings
- Reconciliation of Serious Adverse Event (SAE), Serious Adverse Device Effect (SADE), Adverse Device Effect (ADE) and Device Deficiency (DD)
- Clean-file process including execution of post-entry checks and listings
- Post clean-file tasks

A web based electronic CRF system, will be used to capture data in this investigation. The eCRF system complies with FDA Title 21 CFR part 11 (ER/ES) requirement.

eCRF training will be given to appropriate personnel at initiation of the investigation site(s).

---

**Investigation Code** **Granulox01** **Final Version** **Approval date** **2019-10-24**

---

The Principal Investigator and other authorized personnel at the site(s) will perform data entry. When entering data on-line checks are incorporated for consistency and validation. Support will be provided for system user questions.

When data has been entered, authorized personnel at Mölnlycke can immediately view the data, send queries if necessary and lock eCRF pages when correct data entry has been verified.

Photos will be uploaded in the eCRF and are marked with the subject code. Uploaded photos shall not contain any information that can reveal the identity of the subject. All uploaded photos will be reviewed by personnel at Mölnlycke and stored in the company database. All data entered in the eCRF will be encrypted. The physical database will be stored in Sweden.

Programs for post-entry checks and data listings will be created and executed for validation of data.

Authorized personnel at Mölnlycke will check each finalised eCRF for completeness so that there are no unexplainable empty fields in the eCRF. This is done in order to prevent incomplete data entry.

A clean-file meeting will be held prior to database lock. All decisions on the evaluability of the data from each individual subject will be made and documented before locking the database for the statistical analysis.

#### **4.3.1 Data Retention**

The medical records of clinical investigation subjects must be retained in accordance with local legislation and in accordance with the maximum period of time permitted by the hospital, institution or private practice.

The Principal Investigator must retain all clinical investigation records during the clinical investigation and for the period required by the applicable regulatory requirements or for at least 20 years after the premature termination or completion of the clinical investigation, whichever is the longer. The Principal Investigator must take measures to prevent accidental or premature destruction of these documents. The Principal Investigator should contact Mölnlycke prior to destruction of any records or reports pertaining to the clinical investigation in order to ensure they no longer need to be retained. In addition, if the Principal Investigator leaves the hospital, he/she should provide Mölnlycke with the name and address of the person who will look after and be responsible for the clinical investigation-related records. If the records will be transferred to another person/party, the transfer must be documented at the investigation site or at Mölnlycke.

### **5. STATISTICAL METHODS AND DETERMINATION OF SAMPLE SIZE AND STATISTICAL ANALYSES**

#### **5.1 Determination of Sample Size**

[REDACTED]

[REDACTED]

[REDACTED]

[REDACTED]

### **5.1.1 Independent interim analysis review committee (IARC)**

An independent interim analysis review committee (IARC) will be appointed to follow the safety monitoring and sample size adjustment of the study.

### **5.1.2 Sample size re-estimation**

After approximately 110 patients have completed the study, the IARC will perform an unblended interim analysis on the primary efficacy variable CCC incidence. From this analysis, the IARC will calculate the conditional power (CP).

The IARC will form a recommendation to either terminate, continue, or adjust sample size, based on the following guidelines:

- Futility: If  $CP \leq 30\%$ , then terminate the study for futility.
- Promising outcome: If  $30\% < CP\% < 80\%$ , then adjust the sample size so that  $CP = 0.80$ .  
The sample size could be increased to maximum 600 subjects.
- Favorable outcome: If  $CP\% > 80\%$ , then do not adjust the sample size.

The sample size re-estimation analysis will not require adjustments of the final primary statistical analysis.

## **5.2 Statistical Analyses**

### **5.2.1 Definition of Study Populations**

Full Analysis Set (FAS): All randomized patients with at least one ordinary follow-up visit will be included in the FAS. The final decisions regarding the FAS population will be taken at the Clean File meeting before database lock.

Per-Protocol (PP) Population: All patients in FAS with no significant protocol violations will be included in the PP population. The final decisions regarding the PP population will be taken at the Clean File meeting before database lock.

Safety Population: All enrolled subjects who received at least application of randomized investigational product (IP) will be included in the safety population.

### **5.2.2 General statistical methodology**

This study will use confirmative and explorative analyses. All confirmative analyses will be based on FAS. Confirmative analysis of primary variables will also be performed based on PP.

Imputing of missing data in outcome variables will generally be used. For confirmative analyses, multiple imputations with Fully Conditional Specification (FCS) will be used for primary efficacy analysis. Confirmative secondary analysis and exploratory analyses will use stochastic imputation with FCS. Missing data on demography and background variables will not be replaced.

The study include testing analysis of the primary variable and sequential testing of selected secondary variables for confirmative analysis.

The study utilized stratified randomization based on site, wound size, and wound duration. This is reflected by a stratified primary analysis adjusted for these variables. For adjusted comparison between the two randomized groups, multivariable logistic regression will be used for dichotomous variables and analysis of covariance for continuous variables.

Continuous variable will be described with mean, SD, median, minimum and maximum and categorical variables with numbers and percentages. For unadjusted and adjusted analyses, mean differences with 95% CI will be calculated. For dichotomous variables, for descriptive purpose, relative risk with 95% CI will also be calculated. All significance analyses will be two-sided and conducted at the 5% significance level.

For unadjusted comparison between the two randomized groups Fisher's exact test will be used for dichotomous variables, Fisher's non-parametric permutation test for continuous variables, Mantel-Haenszel chi-square test for ordered categorical variables, and Chi-Square test for non-ordered categorical variables.

Applicable descriptive statistics and non-parametric statistical test methods are used to describe and explore secondary variables. For explorative analyses, no multiple-test considerations are made. For time to endpoint outcomes the Kaplan-Meier model and logrank test are used unadjusted and Cox proportional hazard model for adjusted analyses.

[figure not shown]
### **5.2.2.1 Primary efficacy analysis**

The primary analysis of comparison of CCC between the two randomized groups will be using binary logistic model at significance level 0.05, on FAS with multiple imputation including the following covariates:

1. Country (as fixed effect)
2. Wound duration (<5 months;  $\geq$ 5 months)
3. Wound area after run-in period (<10 cm^2;  $\geq$ 10 cm^2)

Sensitivity analysis will be comparison between the two randomized groups unadjusted on CCC with Fisher's exact test without imputation.

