**90WAR** **90% Wound Area Regression****VLU** **Venous Leg Ulcer****Wound-QoL Wound Quality of Life questionnaire**

## 1. INTRODUCTION

Venous leg ulcer (VLU) is a severe clinical manifestation of chronic venous insufficiency (CVI) and is responsible for about 70% of chronic ulcers in the lower limbs. VLUs are a major health problem because of their high prevalence and associated high cost of care.

Compression therapy is the most widely used conservative treatment for VLUs as the application of external pressure to the calf muscle raises the interstitial pressure resulting in improved venous return and reduction in the venous hypertension. Published healing rates of VLUs obtained with compression therapy vary widely from 40-88%. Over a quarter of patients with VLUs fails to heal despite standard of care including compression therapy, and those who do heal often take 6 months or longer. Risk factors, such as wound age and size, have been identified to be correlated with the failure of VLUs to heal, showing VLUs present for at least 5 months prior to appropriate management and whose area is 10 cm^2 or larger, have less than 20% chance to heal at 24 weeks.

Granulox® is a haemoglobin spray that can be added to standard of care of chronic wounds. It is expected to improve the tissue repair process by increasing tissue oxygen supply. In a previous randomized controlled trial (RCT) comparing Granulox® to a control group in VLUs, a significant mean reduction of the wound surface area was observed at 13 weeks with a decrease of 53.4% (p<0.0001) for Granulox® treated wounds. Use of Granulox® was associated with significant pain score reduction compared to standard wound care alone thus improving patients' quality of life. Furthermore, use of Granulox® as an adjunct therapy led to a significant reduction of slough and recurrence compared with standard care alone.

[figure not shown]
This study is intended to assess the healing benefits of Granulox® therapy in combination with standard of care for the management of chronic VLUs over a period of 20 weeks, compared to VLU standard of care treatment without Granulox®.

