#### 3.2 Procedures and Assessments

This study starts with a 14 days run-in period to verify two of the required inclusion criteria, i.e. that the wound area does not decrease more than 30% during run-in period and compliance to compression therapy part of standard of care.

After the 14-days run-in period during which time patients will receive standard of care, (D-14 to D0) patients meeting the selection criteria will be randomly allocated (on D0) to experimental (i.e. standard of care plus Granulox®) or control (i.e. standard of care only) groups.

Randomization will be stratified on study site, wound duration (<5 months; ≥5 months), and wound area after run-in period (<10; ≥10 cm^2), to ensure equal distribution of test and control in these sub-groups. This, as wound duration and wound area may significantly impact outcomes, and as minor variations in standard of care between study sites may still be present in spite of the measures taken to ensure standardization. See details on standardization of standard of care in Section 3.5.

Each patient will be followed to wound closure, or up to 20 weeks (whichever occurs first), with scheduled clinical visits at 1 week (W1), 4 weeks (W4), 8 weeks (W8), 12 weeks (W12), 16 weeks (W16), and 20 weeks (W20). Additional visits are allowed in between the per-protocol scheduled visits. If suspected wound closure occurs at any point during the study, a final assessment visit will be scheduled 15 days (±3 days) subsequent to the suspected wound closure observation to verify CCC. If wound closure is confirmed, the study is completed for this patient. If wound closure is not confirmed, the patient should continue to be followed according to the schedule of assessments. See study Flow Chart at Section 3.2.1 and Schedule of Assessment at section 3.3.8.

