### **3.8 Efficacy Analyses**

#### **3.8.1 Primary Efficacy Analysis**

The primary analysis will be the comparison of Confirmed Complete wound Closure (CCC) between the two randomized groups using two-sided binary logistic regression analysis at

significance level 0.05, on FAS with multiple imputation including the following stratified covariates:

- Country (as fixed effect)
- Wound duration (<5 months;  $\geq$ 5 months)
- Wound area after run-in period ( $<10$  cm $^2$ ;  $\geq$ 10 cm $^2$ )

Complementary analyses will also be performed for CCC between the two groups on the PP population.

Complementary analyses will also be performed for EOCR (CCC+PCC) between the two groups on the FAS population.

If baseline confounders are found, variables that differ clinically between the two randomised groups and has a causal relation to the primary outcome variable, then complementary analyses will be performed adjusted also for these variables with the same methods as for primary analysis.

Adjusted and unadjusted mean % differences between the two groups in CCC will also be given. The percentage of CCC in each group with 95% exact CI will be calculated. Unadjusted primary analyses of CCC by country and by country and centre will be presented with percentage and mean percent difference with 95% CI.

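### Optional efficiency gain, not an error: the primary logistic model uses wound area only as a split at 10 cm², although planimetry supplies a numeric area at D0

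*Protocol*

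**What the plan says.** Protocol 5.2.2.1 specifies a "binary logistic model at significance level 0.05, on FAS with multiple imputation including the following covariates". The covariates are country as a fixed effect, duration below or from 5 months, and area after run-in below or from 10 cm². SAP 3.8.1 gives the same model ("significance level 0.05, on FAS with multiple imputation including the following stratified covariates"), as does SAP 3.1. No visible text enters area or duration as a numeric term.

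The plan treats both variables as prognostic. Protocol 3.2 stratifies "as wound duration and wound area may significantly impact outcomes". Protocol section 1 states that ulcers of at least 5 months and at least 10 cm² "have less than 20% chance to heal at 24 weeks".

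Numeric area is planned. Protocol 3.3.2.1 and SAP 2.2.1 have each wound picture quantified blind with PictZar, and the schedule in Protocol 3.3.8 places this at D-14 and D0. Protocol 3.4.1 admits areas of 3 to 70 cm² and requires that the area "should not have decreased by more than 30% during the 2-week run-in period". Duration is a history item in SAP 2.1.2, with no unit or precision given.

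Two further rules matter. Protocol 5.2.2 says: "Missing data on demography and background variables will not be replaced". SAP 3.8.1 opens the model to other baseline terms only in complementary analyses and under a condition: "If baseline confounders are found, variables that differ clinically between the two randomised groups". SAP 3.2 on missing data has no visible text, so nothing can be said about what the imputation model contains.

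**The concern.** A two-level split treats a 10 cm² and a 70 cm² ulcer as equally likely to close, and likewise a 3 cm² and a 9 cm² ulcer. If the chance of closure falls steadily with size, the split leaves part of a known prognostic factor unexplained, and the treatment test loses some power. The complementary confounder models do not recover it, because they depend on observed imbalance and leave the primary test unchanged. Only efficiency is at stake. The estimate is not biased by randomisation or by the choice of split, and the measurement needed is already scheduled.

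**Working it through.** 1. **The plan's own figure.** N = 254 cannot be reproduced, because the inputs in Protocol 5.1 are blacked out. Solving in reverse for 127 per arm, 80% power and two-sided 5%, with n = [1.96√(2p̄q̄) + 0.8416√(p₁q₁ + p₂q₂)]² / (p₂ − p₁)²: for 40% v 57.5%, (1.96 × 0.7069 + 0.8416 × 0.6960)² / 0.175² = 3.886 / 0.0306 = 127. The pairs 30% v 47.0% and 50% v 67.2% fit equally well. Healing rates are therefore assumptions below.

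2. **What the split ignores.** If log-odds of closure change by β per log unit of area, the odds ratio across the upper category is (70/10)^β and across the lower is (10/3)^β:
   - weak, β = −0.3: 0.56 and 0.70
   - moderate, β = −0.6: 0.31 and 0.49
   - strong, β = −1.0: 0.14 and 0.30

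3. **Simulation.** N = 254, complete outcomes, 8,000 trials per scenario, Wald test, all models fitted to the same trials. Assumed: area log-normal (median 9 cm², log-SD 0.9) cut to 3–70 cm²; duration log-normal (median 7 months, log-SD 1.0) cut to the eligible range; 7 countries (logit SD 0.3); blocks of 4 within strata. The standard error of each gain is 0.13 to 0.28 points. The area-alone column also takes in a repeat with 3,000 trials per scenario.

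| Prognosis (log-odds per log unit, area / duration) | Log area alone, gain | Both log terms, 40% v 57% | Both log terms, 30% v 46% |
|---|---|---|---|
| Weak (−0.3 / −0.2) | 0 to +0.2 | 80.9 → 81.0% | 77.3 → 77.5% |
| Moderate (−0.6 / −0.4) | 0 to +0.6 | 81.4 → 82.1% | 78.6 → 79.2% |
| Strong (−1.0 / −0.7) | +1.1 to +1.2 | 83.0 → 85.1% | 80.3 → 82.4% |
| True step at the cut-points | −0.1 | −0.1 to 0.0 (gain) | −0.1 to 0.0 (gain) |

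   In the repeat, both terms gave +0.3 to +0.6 (weak or moderate) and +1.6 to +1.9 (strong). As a share of N, both terms are worth 0.4%, 2% and 5% (weak, moderate, strong), that is about 1, 5 and 13 of 254 patients.

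4. **Different assumptions.** A separate simulation of both terms set strength as an odds ratio per SD of each covariate and 80% unadjusted power. It gave +0.3 to +0.8 (1.3 per SD), +0.9 to +1.3 (1.6) and +1.8 to +2.5 (2.0). With 90% base power the last was +1.3. With the conditional odds ratio held fixed instead of the marginal rates, the three were +0.5, +1.4 and +3.0. Replacing the splits by log terms cost about 2 points under a step truth, so the splits should stay.

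5. **Type I error.** In 16,000 null trials per scenario the planned model and the model with both log terms each ran at 5.1 to 5.7%, with a paired difference of −0.02 to +0.04 (SE 0.10 to 0.13). In the separate simulation (8,000 null trials) one of three scenarios gave 5.6% v 6.1%; the larger runs did not show such a gap. Area alone showed no inflation relative to the planned model. With both tests calibrated to 5%, both terms gained +2.3 (strong, 40% control), +0.8 (moderate, 40%) and +0.2 (moderate, 30%).

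6. **Numeric duration.** With both terms, the gain for strong prognosis at 40% control / moderate at 30% control is:
   - 5% of durations missing and those patients dropped: +0.1 / −1.4
   - 10% missing and dropped: −1.9 / −3.7
   - 10% missing, filled with the category mean: +2.0 / +0.5

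**The case against.** Adjusting for the stratification factors in the form used to randomise is standard practice. The only quantitative prognostic statement in the documents, the figure in Protocol section 1, uses exactly the planned cut-points; if prognosis really steps there, nothing is gained. That stands. In the simulations a rate near or below 20% in large, old ulcers arose with moderate prognosis at 30% control closure (20%), but also with step relations (17% at either control rate), so the figure does not settle the matter.

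The design as it will run was not simulated. Multiple imputation was left out, and so was the re-estimation, although "The sample size could be increased to maximum 600 subjects". The power points therefore describe a fixed trial of 254 and not this trial's operating characteristics. That also stands.

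The Wald test was slightly liberal in both models: 5.7% is (5.7 − 5.0)/0.17 = 4.1 standard errors above 5% in 16,000 trials. A few tenths of a point of the uncalibrated gains may come from this, and no calibrated figure was produced for area alone.

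The documents name more than one size measure: PictZar in Protocol 3.3.8 and SAP 2.2.1, Tissue Analytics in the SAP schedule, and an estimated size in SAP 2.1.5. An amendment must say which one it means. For duration, the rule that missing background data are not replaced could turn a gain into a loss. Both objections shape the recommendation but do not remove it for area.

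**Conclusion.** The planned model is sound, and leaving it unchanged is acceptable. Adding log planimetric D0 area is a small, cheap improvement: about 0 to 0.6 points of power if within-category prognosis is weak or moderate, about 1.2 if strong, and about zero under a step at the cut-point. The smallest of these gains cannot be told from zero. With log duration as well, the gain is about 0 to 1 point (weak or moderate) and about 1.5 to 2.5 (strong), provided patients are not lost. All of this rests on assumed healing rates, covariate distributions and prognostic strength.

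A reader might infer three stronger claims that the documents do not support:
- **That the primary analysis is wrong or the trial underpowered.** The analysis adjusts for the stratification factors, and no shortfall can be shown while the sample size inputs are blacked out.
- **That about 4 points are to be had.** Simulated gains of that size needed slopes 1.7 times the strong ones (87.4 → 91.2% at 40% control). These imply control closure of 96% for a 3 cm², 2-month ulcer and 0.2% for a 70 cm², 60-month ulcer. Nothing in the documents shows prognosis of that strength.
- **That duration should be added on the same footing.** The documents do not assure a complete numeric value.

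**What to change.** If the option is taken, before any unblinded look (the interim comes at about 110 completed patients):

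1. In Protocol 5.2.2.1 and SAP 3.1 and 3.8.1, keep country and both splits and add log(PictZar planimetric wound area at D0). Keep the splits-only model as a sensitivity analysis.
2. Use the same term in the FCS imputation model if it is not already there.
3. State how a patient with an unreadable D0 picture stays in the primary analysis, since missing background values are otherwise not replaced.
4. Add log(wound duration) only if a numeric duration is confirmed to be collected for essentially all patients.

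The cost is wording in two documents and possibly an ethics committee notification under Protocol 6. There are no new visits or measurements. The downsides are an approximate log-linearity assumption and a slightly different conditional odds ratio (with both terms, the simulated mean moved from 2.11 to 2.14 under weak and from 2.25 to 2.39 under strong prognosis).

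As a separate item that lends no weight to this one: Protocol 3.2 and 5.2.2 say randomisation is stratified by site, while Protocol 3.4.3 and SAP 1.2.1 and 3.1 say country. The wording should be reconciled to the scheme actually used.
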